2.3 Exploratory Objective

CI

3 STUDY DESCRIPTION

3.1 Summary of Study Design

This is a Phase 2, open-label, dose-finding, 3-period, 3-treatment study using successively escalating doses of 300 mg, 600 mg, and 900 mg gemcabene in patients with HoFH. All patients will be on each of the successive doses for 4 weeks at a time. Patients will remain on their current stable, lipid-lowering therapy throughout the study. Patients will not be allowed in the study if they are undergoing apheresis or taking mipomersen or lomitapide.

Efficacy, PK, and safety data from this study will be used along with previously completed studies and a planned randomized, placebo-controlled study in patients with hypercholesterolemia (GEM-301) to confirm the appropriate dose of gemcabene for use in Phase 3 studies. An effective dose is defined as a dose that achieves $\geq 15\%$ mean reduction in LDL-C after 4 weeks of treatment with the study totaling 12 weeks of treatment.

Approximately 8 patients will be enrolled into the study. Total study duration will be up to 18 weeks and will consist of a Screening Visit, a Treatment Period, and a Follow-up Visit.

The Screening Visit will occur up to 14 days prior to Day 1. Patients will sign the informed consent form (ICF) prior to any study procedures being performed. Patients must meet all of the inclusion and none of the exclusion criteria to be eligible for study participation.

The Treatment Period is a sequential design whereby each patient will receive gemcabene 300 mg QD for 4 weeks. The same patients will then receive a 600 mg dose QD for 4 weeks and finally 900 mg dose QD for 4 weeks. There will be no interruptions in gemcabene dosing when changing from the 300 mg to the 600 mg dose or when changing from the 600 mg to the 900 mg dose unless there are clinically significant safety issues resulting in the temporary or permanent discontinuation of study drug. The first 300 mg dose of study drug will be administered at the site on Day 1. For days when patients will self-dose, they will be instructed to take study drug at the same time each morning on an empty stomach 30 to 60 minutes prior to breakfast. For patients also taking bile acid sequestrants, study drug should be taken at least 2 hours before administration of bile acid sequestrants. Assessments will be performed after the patient has been on the study drug for 2 weeks for each dosing level and on the last day of each dose.

For each escalated dose, percent change from baseline in LDL-C will be calculated using the baseline LDL-C value and the final LDL-C value measured for each dose. Baseline will be defined as the average of the Screening Visit occurring up to 14 days prior to Day 1 and Day 1 (pre-dose) measurements.

Pharmacokinetic samples will be collected pre-dose (must be 24 ± 2 hours from the previous day's dose) and 0.5, 1, 2, 3, 5, and 12 hours post-dose on Day 28, Day 56, and Day 84 in collection tubes containing dipotassium ethylenediaminetetraacetic acid (K₂EDTA) as the anticoagulant; for determination of gemcabene repeat-dose PK parameters, steady state is assumed following QD administration for 28 days and therefore, plasma gemcabene concentrations at 24 hours post-dose are considered to be equal to pre-dose concentrations. For all other study visits where routine plasma drug monitoring will be performed (Day 1, Day 14, Day 42, Day 70, and the Early Termination [ET] Visit, if applicable), samples will be collected pre-dose (must be 24 ± 2 hours from the previous day's dose if a previous day's dose occurred).

The Follow-up Visit will occur 4 weeks (± 3 days) after the last dose of study drug.

3.2 Study Indication(s)

The indication for this study is for the treatment of hypercholesterolemia, specifically patients with HoFH.

4 SELECTION AND WITHDRAWAL OF PATIENTS

4.1 Inclusion Criteria

Patients who meet all of the following criteria will be eligible to participate in the study:

1. Provision of written and signed informed consent (by patient or legal guardian) prior to any study-specific procedure;
2. Male or female ≥ 17 years of age at time of consent;
3. Diagnosis of HoFH by genetic confirmation (including compound heterozygosity) or a clinical diagnosis based on either (1) a history of an untreated LDL-C concentration >500 mg/dL (12.92 mmol/L) together with either appearance of xanthoma before 10 years of age, or evidence of heterozygous familial hypercholesterolemia in both parents or, if history is unavailable, (2) LDL-C >300 mg/dL (7.76 mmol/L) on maximally tolerated lipid-lowering drug therapy;
4. Currently on a stable, low-fat, low-cholesterol diet in combination with a pre-existing, regulatory-approved, not excluded lipid-lowering therapy (i.e., statins, monoclonal antibodies to PCSK9, cholesterol-absorption inhibitors, bile acid sequestrants, or nicotinic acid, or any combination thereof) at a stable dose for at least 4 weeks prior to the Screening Visit;
5. Fasting LDL-C value >130 mg/dL (3.36 mmol/L) at the Screening Visit;
6. Physical examination, including vital signs, that is within normal limits or clinically acceptable to the Investigator;
7. Weight ≥ 50 kg;
8. Female patients must not be pregnant or lactating. Women of child-bearing potential must have a negative serum pregnancy test at the Screening Visit and negative urine dipstick on Day 1 prior to dosing in order to qualify for the study. Women who are surgically sterile or are clinically confirmed to be post-menopausal (i.e., documented amenorrhea for ≥ 1 year in the absence of other biological or physiological causes) are not considered to be of child-bearing potential; and
9. Women of child-bearing potential must agree to use acceptable methods of contraception throughout the duration of the study and for 30 days after the last dose of study drug. For this study, double-barrier contraception is required.

4.2 Exclusion Criteria

Patients who meet any of the following criteria will be excluded from participation in the study:

1. Other forms of primary hyperlipoproteinemia and secondary causes of hypercholesterolemia (e.g., nephrotic syndrome or hypothyroidism);
2. Abnormal liver function test at the Screening Visit (aspartate aminotransferase or alanine aminotransferase $>2 \times$ the upper limit of normal [ULN]; total bilirubin $>1.5 \times$ ULN; or alkaline phosphatase $>2 \times$ ULN based on appropriate age and gender normal values). Patients with bilirubin $>1.5 \times$ ULN and history of Gilbert's syndrome may be included; reflexive direct bilirubin testing will be used to confirm Gilbert's syndrome;

3. Moderate (Grade B) or severe (Grade C) chronic hepatic impairment according to the Child-Pugh classification;
4. Active liver disease (e.g., cirrhosis, alcoholic liver disease, hepatitis B virus [HBV], hepatitis C virus [HCV], autoimmune hepatitis, liver failure, liver cancer), history of liver transplant, or known diagnosis of human immunodeficiency virus (HIV);
5. Triglycerides value >400 mg/dL (4.52 mmol/L) at the Screening Visit;
6. Moderate to severe renal insufficiency defined as an estimated GFR <30 mL/min/1.73 m² (calculated using The Chronic Kidney Disease Epidemiology Collaboration equation) at the Screening Visit;
7. Abnormal urinalysis (proteinuria greater than trace or any male or non-menstruating female with greater than trace hematuria), confirmed by reflexive urine protein:creatinine ratio testing;
8. Uncontrolled thyroid disease: hyperthyroidism or hypothyroidism as defined by thyroid-stimulating hormone (TSH) below the lower limit of normal or >1.5 × ULN, respectively, at the Screening Visit. If controlled, treatment should be stable for at least 3 months prior to the Screening Visit;
9. Type 1 diabetes mellitus or uncontrolled type 2 diabetes mellitus (hemoglobin A1c [HbA1c] value >8%), or any diabetic patient taking insulin and/or thiazolidinediones;
10. New York Heart Association Class III or IV heart failure (see [Appendix C](#));
11. Myocardial infarction, severe or unstable angina pectoris, coronary angioplasty, coronary artery bypass graft, or other major cardiovascular events resulting in hospitalization within 3 months of the Screening Visit. Patients with adequately treated stable angina, per Investigator assessment, may be included;
12. Uncontrolled cardiac arrhythmia or prolonged QT on the Screening Visit or Day 1 prior to dosing ECG (QTcF >450 msec for men and >470 msec for women) or known family history of prolonged QT or unexplained sudden cardiac death;
13. Uncontrolled hypertension, defined as sitting systolic blood pressure >180 mmHg or diastolic blood pressure >110 mmHg, and confirmed by repeat measurement;
14. Currently receiving cancer treatments or, in the Investigator's opinion, at risk of relapse for recent cancer;
15. Use of fibrate lipid-lowering agent 6 weeks prior to the Screening Visit;
16. Hypersensitivity to or a history of significant adverse reactions to any fibrate lipid-lowering agent;
17. Use of apheresis (LDL or plasma) 8 weeks prior to the Screening Visit;
18. Use of lomitapide 2 months prior to the Screening Visit;
19. Use of mipomersen 5 months prior to the Screening Visit;
20. Use of any excluded medications or supplements (e.g., potent cytochrome P450 [CYP] 3A4 inhibitors, see [Appendix D](#));

21. History of drug or alcohol abuse within the past year or inability to comply with protocol requirements, including subject restrictions (see [Section 5.6.3](#));
22. Previously treated with gemcabene;
23. Participation in another clinical study of an investigational agent or device concurrently or within 1 month prior to the Screening Visit, or use of an investigational agent within 1 month or 5 half-lives (if known), whichever is longer, prior to the Screening Visit; or
24. Any other finding which, in the opinion of the Investigator, would compromise the patient's safety or participation in the study.

4.3 Withdrawal Criteria

Participation of a patient in this clinical study may be discontinued for any of the following reasons:

- The patient withdraws consent or requests discontinuation from the study for any reason;
- Occurrence of any medical condition or circumstance that exposes the patient to substantial risk and/or does not allow the patient to adhere to the requirements of the protocol;
- Any SAE, clinically significant adverse event, severe laboratory abnormality, concomitant illness, or other medical condition which indicates to the Investigator that continued participation is not in the best interest of the patient;
- Pregnancy;
- Requirement of prohibited concomitant medication;
- Patient failure to comply with protocol requirements or study-related procedures; or
- Termination of the study by the Sponsor or the regulatory authority.

If a patient withdraws prematurely from the study due to the above criteria or any other reason, study staff should make every effort to complete the full panel of assessments scheduled for the ET Visit. The reason for patient withdrawal must be documented in the electronic Case Report Form (eCRF).

In the case of patients lost to follow-up, attempts to contact the patient must be made and documented in the patient's medical records.

Withdrawn patients will not be replaced unless the number of withdrawn patients study-wide is >2 . If >2 patients are withdrawn from the study, then replacement patients will be enrolled to ensure ≥ 6 patients complete the entire study (the entire Treatment Period).

5 STUDY TREATMENTS

5.1 Treatment Groups

During the 12-week Treatment Period, all patients will receive gemcabene 300 mg QD for 4 weeks, followed by 600 mg QD for 4 weeks, followed by 900 mg QD for 4 weeks.

5.2 Rationale for Dosing

Based on the results from a completed clinical study (Study 1027-018), oral gemcabene significantly lowered LDL-C with mean percent changes of -24% and -28% at 300 mg and 900 mg, respectively, compared to -6% in the placebo group in hypercholesterolemic patients on stable statin therapy.

Gemcabene was observed to be well tolerated at single doses up to 1500 mg and multiple doses up to 900 mg. This included 837 subjects and patients with varying underlying conditions who received multiple doses of up to 900 mg for up to 12 weeks. Adverse events were generally mild to moderate in intensity with no treatment-related SAEs reported.

5.3 Randomization and Blinding

This is an open-label study, therefore, no randomization or blinding is necessary.

5.4 Breaking the Blind

This is an open-label study, therefore, no blinding is necessary.

5.5 Drug Supplies

5.5.1 Study Drug Identification

Established names	Gemcabene calcium – parent gemcabene
CAS registry number	209789-08-2 – parent 183293-82-5
Chemical class	Anti-hypercholesterolemic
Chemical name	6,6'-oxybis (2,2-dimethylhexanoic acid) monocalcium salt - parent 6,6'-oxybis(2,2-dimethylhexanoicacid)
Molecular formula	$C_{16}H_{28}O_5\cdot Ca$ – parent $C_{16}H_{30}O_5$
Molecular weight	340.48 – parent 302.408
Drug name/formulation/concentration	Gemcabene (parent)/tablets/300 mg
Manufacturer (drug substance)	CI [REDACTED]
Manufacturer (drug product)	CI [REDACTED]
Storage requirements	Room temperature ($20 \pm 5^\circ C$) in a secured location (locked) with no access for unauthorized personnel.

5.5.2 Formulation and Packaging

The tablet drug product for oral administration is an immediate-release tablet containing **Cl**

Study drug will be packaged in high-density polyethylene bottles with child-resistant closures. Patients will take the following for each of the 3 dose levels:

- 300 mg: one 300 mg tablet orally QD,
- 600 mg: two 300 mg tablets orally QD, and
- 900 mg: three 300 mg tablets orally QD.

5.5.3 Study Drug Preparation and Dispensing

Study drug will be administered at the site on days when study visits occur during the Treatment Period. Patients will self-dose at all other times during the Treatment Period. The Investigator or designee will provide patients with sufficient study drug until the next scheduled study visit.

5.5.4 Study Drug Administration

Patients will be instructed to take study drug at the same time in the morning on an empty stomach 30 to 60 minutes prior to breakfast. Missed doses will be documented. For patients also taking bile acid sequestrants, study drug should be taken at least 2 hours before administration of bile acid sequestrants. If a patient misses a dose, only a single dose (and not 2 doses) should be taken on the following day.

5.5.5 Treatment Compliance

Patients will be instructed to take study drug daily according to the protocol and return used and unused packaging to the site at each subsequent study visit.

Compliance with administration of study drug will be assessed by means of tablet counts based on the assessment of empty bottles returned to the site at each study visit after Day 1 during the Treatment Period and the ET Visit, if applicable. Tablet counts will be recorded on the appropriate eCRF and the drug accountability log.

The Investigator or designee will remind patients at each visit of the importance of following the protocol-defined schedule for taking study drug. Reasons for not following the study drug administration schedule as described in the protocol will be clearly recorded in the source documents.

5.5.6 Storage and Accountability

The study drug will be stored at room temperature ($20 \pm 5^\circ\text{C}$) in a secured location (locked) with access restricted to authorized personnel only. Storage temperature will be monitored and recorded.

Upon receipt of study drug, the Investigator or designee will conduct a complete inventory of all study drug and ensure no damage occurred during shipment.

The Investigator will maintain adequate records documenting the receipt, use, loss, or other disposition of study drug. Drug accountability logs will identify the study drug code number and account for the disposition on a patient-by-patient basis, including specific dates and quantities. The drug accountability logs will be signed by the individual who dispenses the study drug and copies will be provided to the Sponsor.

All used and unused supplies will be appropriately inventoried and verified by the clinical research associate (CRA).

Unused study drug may be destroyed at the sites according to their Standard Operating Procedures (SOPs). If a site does not have appropriate SOPs for compliance, the study drug will be returned to the Sponsor at the end of the study.

5.6 Prior and Concomitant Medications and/or Procedures

5.6.1 Permitted Medications and/or Procedures

Patients are required to be on a stable, low-fat, low-cholesterol diet in combination with a pre-existing, regulatory-approved, not excluded lipid-lowering therapy (i.e., statins, monoclonal antibodies to PCSK9, cholesterol-absorption inhibitors, bile acid sequestrants, or nicotinic acid, or any combination thereof) during the study.

5.6.2 Excluded Medications and/or Procedures

Patients are not permitted to receive treatment with lomitapide 2 months prior to the Screening Visit, mipomersen 5 months prior to the Screening Visit, or a fibrate lipid-lowering agent 6 weeks prior to the Screening Visit. Patients are not permitted to use strong CYP3A4 inhibitors while on the study drug. See [Appendix D](#) for a specific list of CYP3A4 inhibitors.

Additionally, plasmapheresis or LDL-apheresis is not permitted 8 weeks prior to the Screening Visit or during the study. Excluded procedures are specified in the exclusion criteria ([Section 4.2](#)).

5.6.3 Restrictions and Dietary Guidelines

It is important that patients are instructed to not undertake any form of strenuous physical activity for at least 24 hours prior to repeat blood testing.

Patients are restricted from using alcohol within 48 hours prior to study visits.

Assessments that require a patient to fast will be defined as no food or caloric beverage for at least 10 hours prior to sample collection. Patients will be permitted to have water. Study drug should be taken at the same time in the morning on an empty stomach 30 to 60 minutes prior to breakfast. For patients also taking bile acid sequestrants, study drug should be taken at least 2 hours before administration of bile acid sequestrants.

Patients will be counseled on maintaining a low-fat, low-cholesterol diet (National Cholesterol Education Program Adult Treatment Panel III [NCEP ATP-III] or equivalent) throughout the study.

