9.6 Clinical Laboratory Evaluations

Clinical laboratory evaluations will be collected at the visits shown in the Schedule of Procedures ([Appendix A](#)) and the data captured will be forwarded to the central laboratory for evaluation. Assessments that require a patient to fast will be defined as no food or caloric beverage for at least 10 hours prior to sample collection. Patients will be permitted to have water.

Central laboratory results will be provided to the sites. Laboratory results that appear potentially spurious based on the Investigator's clinical assessment and review of the patient's medical history may be repeated for confirmation of the finding. Reassessments of non-qualifying screening labs must be reviewed and approved by the Medical Monitor prior to obtaining the new specimen. The clinical rationale for performing repeat testing of screening assessments should be thoroughly documented.

Standard clinical laboratory evaluations for safety chemistry, coagulation, and hematology will be conducted at all study visits and the Follow-up Visit (only for patients who had an abnormal result at Day 84 [or the ET Visit, if applicable] or an ongoing treatment-related adverse event). Clinically significant abnormal creatinine results at Day 84 (or the ET Visit, if applicable) will also be followed-up 2 weeks (± 3 days) after the last dose of study drug in addition to the 4 week (± 3 days) Follow-up Visit. See [Appendix B](#) for a list of clinical laboratory analytes and description of when repeat or reflexive testing will be required.

A fasting lipid panel will be assessed at all study visits, excluding the Follow-up Visit. Fasting apolipoproteins, hsCRP, and fibrinogen will be assessed at Day 1, Day 28, Day 56, Day 84, and the ET Visit, if applicable. In addition to these lipid parameters, CI will also be measured at Day 1, Day 84, and the ET Visit, if applicable.

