APPENDIX B: CLINICAL LABORATORY ANALYTES

Standard Safety Chemistry Panel

Alanine aminotransferase	Albumin
Alkaline phosphatase	Aspartate aminotransferase
Bicarbonate	Blood urea nitrogen
Calcium	Chloride
Creatine kinase	Creatinine [1]
Gamma-glutamyl transferase	Glucose
Lactate dehydrogenase	Phosphorus
Potassium	Sodium
Total bilirubin [2]	Total protein

Estimated glomerular filtration rate (GFR) [3]

1. For a creatinine increase of >0.3 mg/dL (27 µmol/L) from baseline during the study, repeat chemistry will be performed.
2. If total bilirubin is elevated, reflexive direct bilirubin testing will be performed.
3. For an estimated GFR decrease of >15 mL/min from baseline during the study, repeat chemistry will be performed.

Additional Chemistry Parameter

Glycosylated hemoglobin

Endocrinology

Thyroid-stimulating hormone

Hematology

Hematocrit	Hemoglobin [1]
Platelet count	Red blood cell count
Mean corpuscular hemoglobin concentration	Mean corpuscular hemoglobin
White blood cell count and differential (basophils, eosinophils, lymphocytes, monocytes, and neutrophils) [2]	Mean corpuscular volume

1. For a hemoglobin decrease of >1.5 g/dL from baseline during the study, repeat hematology studies and reflexive evaluation of reticulocyte count will be performed.
2. Manual microscopic review is performed only if white blood cell count and/or differential values are out of reference range.

Urinalysis [1]

pH	Proteinuria [2]
Ketones	Blood
Leukocyte esterase	Specific Gravity
Glucose	Bilirubin
Nitrite	Neutrophil gelatinase-associated lipocalin (NGAL) [3]

1. A urine microscopic examination will be performed when dipstick results are abnormal (positive for blood, leukocyte esterase, or nitrites).
2. Urine protein:creatinine ratio will be performed at the Screening Visit, Day 1, Day 28, Day 56, Day 84, the Follow-up Visit (only for patients who had an abnormal result at Day 84 [or the ET Visit, if applicable] or an ongoing treatment-related adverse event), and the ET Visit, if applicable.
3. Urinary NGAL will be measured at Day 1, Day 28, Day 56, Day 84, the Follow-up Visit (only for patients who had an abnormal result at Day 84 [or the ET Visit, if applicable] or an ongoing treatment-related adverse event), and the ET Visit, if applicable.

Pregnancy Test

Serum and urine pregnancy tests will be administered to all female patients of child-bearing potential.

Serology

Hepatitis B	Hepatitis C
Human Immunodeficiency Virus	

Coagulation

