APPENDIX E: MUSCLE INJURY AND HEPATIC MONITORING

Muscle Injury

Muscle injury will be assessed using a combination of clinical signs and symptoms and laboratory data (creatinine kinase [CK], hepatic, and renal function).

All patients with suspected or confirmed muscle injury should be managed according to the standard of care at the discretion of the Investigator.

- Patients with new or unexplained muscle symptoms should have an unscheduled visit scheduled within 7 days of site notification. At this visit, samples should be sent for a full chemistry panel, including CK, liver, and renal function.
- Patients with CK elevations of $>3 \times$ upper limit of normal (ULN) who are asymptomatic should be considered for an unscheduled visit (+ isozymes), based upon medical judgment.
- All patients with CK elevations $>10 \times$ ULN should have an unscheduled visit (+ isozymes). Study drug should be temporarily discontinued, pending the results of an investigation into the cause of muscle injury and/or CK elevation is complete.

It is important that patients are instructed to not undertake any form of strenuous physical activity for at least 24 hours prior to repeat blood testing.

Hepatic Monitoring

Patients with hepatic enzyme elevations should be managed according to the standard of care, at the discretion of the Investigator. For patients with signs or symptoms suggestive of hepatitis, an unscheduled visit and a chemistry panel should be performed. Patients with an alanine aminotransferase (ALT) $>2 \times$ ULN with symptoms suggestive of hepatitis should have an unscheduled visit. Patients with ALT $>3 \times$ ULN with or without symptoms should also have an unscheduled visit. A repeat assessment should be performed as soon as possible to confirm the finding. A clinical evaluation should be performed, including assessment of past medical history (including non-alcoholic fatty liver disease/steatohepatitis and alcohol use) and concomitant medications (including over the counter drugs and herbal supplements). Risk factors for hepatitis infection should be reviewed and hepatitis studies should be performed.

Study drug should be temporarily discontinued during this evaluation if the patient has signs or symptoms of hepatitis or an ALT $>5 \times$ ULN. The possible dosing re-initiation (re-challenge) or follow-up schedule for any events meeting these criteria will be determined by the Investigator in consultation with the Medical Monitor.

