### **5.2 Assessment Windows**

To summarize laboratory variables, consecutive time windows will be created around each planned visit. In the descriptive statistics of laboratory variables, only measurements from scheduled visits will be used if values are available. If no values from a scheduled visit are available but values from unscheduled visits are available, the values from the last unscheduled visit from that window will be used for the summary statistics. The results of all laboratory values from unscheduled and repeat measurements will be recorded in the clinical database. In listings and narratives, all laboratory values including unscheduled and repeat values will be included.

For analysis purposes, if the event date is on or after the first treatment date, the study day is defined as follows:

$$\text{Study Day} = \text{Event date} - \text{First treatment date} + 1$$

Therefore, the day of first treatment will be Day 1. If the event date is prior to the first treatment date, the addition of 1 will not be included in the calculation; thus, there will be no Day 0.

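### The 24-hour exertion restriction covers only repeat blood tests, although the scheduled CK is the value that can start the temporary drug hold and that enters the laboratory summaries

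*Protocol*

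**What the plan says.** Two places in the protocol carry the exertion instruction, and both attach it to repeat testing. Section 5.6.3 tells patients to "not undertake any form of strenuous physical activity for at least 24 hours prior to repeat blood testing". Appendix E, directly after its CK rules, again bars "strenuous physical activity for at least 24 hours prior to repeat blood testing". The sentence that follows in section 5.6.3 uses a wider scope for alcohol: "Patients are restricted from using alcohol within 48 hours prior to study visits".

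CK is part of routine sampling. Appendix B lists "Creatine kinase" in the standard safety chemistry panel, and section 9.6 says: "Standard clinical laboratory evaluations for safety chemistry, coagulation, and hematology will be conducted at all study visits".

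Appendix E acts on CK at two levels:
- Above 3 times the upper limit of normal (ULN) without symptoms, an unscheduled visit is considered on medical judgment. No hold is stated.
- Above 10 times ULN, every patient has an unscheduled visit, and the rule reads: "Study drug should be temporarily discontinued, pending the results of an investigation into the cause of muscle injury and/or CK elevation is complete". No confirming test is asked for before the hold.

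For descriptive laboratory statistics, SAP section 5.2 (repeating protocol section 10.2.2) says that "only measurements from scheduled visits will be used if values are available". Unscheduled and repeat values go into listings and narratives. SAP section 8.3 adds change from baseline and counts of new or worsened abnormalities.

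**The concern.** By placing the restriction among the muscle-injury rules, the protocol accepts that recent exertion can distort the bloods used to judge muscle injury. It then applies the control only to the later, confirmatory sample. The sample that can start the hold, and that is tabulated, is the uncontrolled one.

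Two things are at stake. CK is the named skeletal-muscle safety variable, so an exertional rise at a scheduled visit would sit in the summaries as an apparent safety finding, and there is no control arm to show how often such values occur without the drug. Less often, a value above 10 times ULN could interrupt dosing for a reason unrelated to the drug, so that the next LDL-C is measured after missed doses.

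**Working it through.** The plan states no figure on this point, so there is nothing to reproduce. The check is a comparison of sections, followed by a bounded illustration.

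**Which samples are covered**

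| Item | Scope or timing | Source |
|---|---|---|
| Exertion restriction, 24 hours | Before repeat blood testing | Protocol 5.6.3, Appendix E |
| Alcohol restriction, 48 hours | Before study visits | Protocol 5.6.3 |
| CK sampling | All study visits | Protocol 9.6, Appendix B |
| Hold at CK above 10 times ULN | On the observed value, no prior confirmation | Appendix E |
| Value in descriptive summaries | Scheduled value if there is one | Protocol 10.2.2, SAP 5.2 |

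The scheduled samples are Screening, Day 1, and Days 14, 28, 42, 56, 70 and 84: 2 + 6 = 8 visits. None is covered by the exertion restriction as written. A rested repeat does not replace the scheduled value in the descriptive statistics. Neither document says whether the repeat would change the abnormality counts.

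**Could a hold come before a primary LDL-C value?** The primary LDL-C visits are Days 28, 56 and 84. Of the six on-treatment CK samples, five (Days 14 to 70) precede a later primary visit, which gives 5 × 8 = 40 samples in 8 patients. A hold prompted by the Day 84 sample cannot affect LDL-C.

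**How often?** The rate of exertional CK above 10 times ULN is not in the documents. With an assumed rate p per sample, and samples treated as independent, the chance of at least one such hold is 1 − (1 − p)^40:

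| Assumed p | Chance of at least one |
|---|---|
| 0.1% | 3.9% |
| 0.5% | 18.2% |
| 1% | 33.1% |
| 2% | 55.4% |

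The spread shows only that the result depends wholly on p.

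**Largest effect on a mean.** Suppose, as an extreme, that one of 8 patients had lost the whole LDL-C effect at a primary visit. The mean then moves by effect ÷ 8. With the prior-study effects in protocol section 5.2:
- 300 mg: 24 ÷ 8 = 3.0 points, from −24% to −21%.
- 900 mg: 28 ÷ 8 = 3.5 points, from −28% to −24.5%.
- With a smaller assumed effect of 24 − 6 = 18 points: 18 ÷ 8 = 2.25 points, from −18% to −15.75%, still beyond the 15% mean reduction that defines an effective dose.

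These are upper bounds. No document says that a short hold removes the whole effect.

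**The case against.** The strongest reply is that the design is coherent as it stands: an unrestricted first sample, then a controlled repeat to find the cause. Several safeguards support this. Appendix E requires the cause of the rise to be investigated, which is where exertion would come to light. Section 9.6 lets the investigator repeat a result that looks spurious. Section 9.1 does not require an unverified abnormal result to be reported as an adverse event. Repeats appear in listings and narratives. It can also be said that repeat was meant in the sense of serial, so that all samples are already covered.

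Much of this stands. The adverse event tables are partly protected and the hold is temporary. The laboratory summaries have no matching protection, because the scheduled value takes precedence there. The serial reading is possible, but the study-visit wording used for alcohol in the next sentence, and the use of repeat for follow-up tests elsewhere in the protocol, favour the narrow one. If the wider sense was meant, sites cannot tell from the text.

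A reader might also infer more than the documents support:
- That exertion could cost a patient the LDL-C endpoint. A temporary hold is not among the withdrawal reasons in section 4.3, scheduled visits go on, and SAP sections 5.3 and 7.1 model every scheduled visit and keep patients with missing values.
- That CK above 3 times ULN stops drug. Appendix E states no hold at that level for patients without symptoms.
- That an exertional Screening value distorts the CK baseline. The Screening and Day 1 average is given for LDL-C and efficacy, and the SAP limits averaging to lipids. Neither document says that Screening supplies the CK baseline.
- That one patient's share of the sample measures the problem. That share is the same for any single-patient event and says nothing about how often this one occurs.

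**Conclusion.** The point holds as a minor one. As written, the exertion control misses all eight scheduled CK samples, while the scheduled value can start the temporary hold above 10 times ULN and is the one kept in the descriptive laboratory summaries. The main consequence is a less interpretable CK summary in an uncontrolled trial of about 8 patients. The secondary one is an occasional dosing interruption before a later LDL-C value, for holds that begin before Day 84.

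The size cannot be fixed from the documents, because the frequency of exertional CK rises is not given. The conclusion rests on reading repeat as confirmatory, and on the protocol's own premise that exertion affects these bloods. It does not rest on the assumed rates or the upper-bound shifts. The documents also do not show how many high values a 24-hour restriction would prevent.

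**What to change.** Reconcile protocol section 5.6.3, Appendix E and SAP section 5.2. Word the existing 24-hour instruction so that it applies before scheduled visits with blood sampling as well as before repeat tests, in the way the alcohol restriction already covers study visits, and use the same wording in both protocol sections and in the patient instructions. SAP section 5.2 can then go on using scheduled values, now taken under the same condition as the repeats. Leave the CK action thresholds and the hold rules as they are.

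The cost is a few words in the protocol and patient instructions. The small downside is 24 hours of restricted activity before each of about eight visits.
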